**EFFECT OF DIFFERENT WEEKLY COMBINED TRAINING FREQUENCIES
ON FUNCTIONAL CAPACITY, HEMODYNAMIC AND ANTHROPOMETRIC
ASPECTS OF ELDERLY PEOPLE WITH CARDIOMETABOLIC RISK
FACTORS**

March 03, 2024

Abstract

Objective: The objective of this study was to compare the effects of two different weekly frequencies of a 12-week combined training period on functional capacity, hemodynamic, and biochemical profile in older people with cardiometabolic risk factors. **Methods:** This is a pragmatic clinical trial. Functional, hemodynamic, and biochemical outcomes were assessed at baseline and after 12 weeks. Participants were divided into two groups: G2x (trained twice a week), and G3x (trained three times a week). Both groups performed the same training program, which consisted of strength and aerobic training with progressive intensity. Data analysis was performed using intention to treat (ITT), employing a 2-way analysis of covariance (ANCOVA) for repeated measures, with the baseline values used as covariates. The significance adopted was 0.05.

1. INTRODUCTION

The population ageing is a global trend that brings significant challenges for promoting health and quality of life, since the prevalence of cardiometabolic risk factors and gradual loss of functional capacity, reduced aerobic fitness, strength, and agility in older adults is more pronounced⁽¹⁾. The presence of risk factors, such as hypertension, diabetes, and dyslipidemia, increases the susceptibility of older people to cardiovascular diseases, which remain one of the leading causes of morbidity and mortality worldwide⁽²⁾. In addition, older adults with cardiometabolic risk factors exhibit lower functional capacities, such as muscle strength, mobility, lower and upper limb power and flexibility, compared to older adults without cardiometabolic risk factors^(3,4).

Exercise is consolidated as a valuable tool for improving functional capacity⁽⁵⁾, cardiovascular health^(6,7), and metabolic and biochemical markers^(8,9) in older adults with cardiometabolic risk factors⁽¹⁰⁾. Although there is a consensus regarding the benefits of exercise for the older population with cardiometabolic risk factors, determining the dose-response of the training for this population still generates uncertainty. Current recommendations suggest performing multicomponent training two to three times per week⁽⁵⁾; however, this variation still raises questions about the most effective weekly frequency to optimize health outcomes in this population.

In this sense, comparisons between strength training frequencies were conducted in postmenopausal women with osteoporosis, showing better outcomes for three sessions per week compared to twice-weekly sessions and a control group⁽¹¹⁾. On the other hand, a clinical trial comparing one, two, and three weekly sessions of combined training in women over 60 years old found no significant differences between the training groups⁽¹²⁾. However, no studies were found comparing different weekly session frequencies of combined training involving individuals with cardiometabolic risk factors.

Thus, the optimization of training prescription through the manipulation of different training variables, such as weekly frequency, still requires further investigation from a functional, cardiovascular, and metabolic perspective. Therefore, this study aims to investigate the effects of two different weekly frequencies of combined training on functional capacity, blood pressure, and biochemical profile in older adults with cardiometabolic risk factors. We hypothesized that performing three weekly sessions of

combined training would lead to better adaptations in cardiovascular risk factors and functional capacity than performing two weekly sessions.

1.1 OBJECTIVES

1.1.2 General Objective

To compare the effect of two different weekly frequencies of combined training on functional capacity, hemodynamic and anthropometric aspects of elderly individuals with cardiometabolic risk factors.

2. METHODS

2.1. EXPERIMENTAL APPROACH TO THE PROBLEM

This study was a pragmatic clinical trial with two intervention groups. Initially, an anamnesis was conducted to collect sociodemographic data and information about the participants health, as well as to investigate their engagement in other physical activities. Subsequently, anthropometric, functional, hemodynamic, and biochemical assessments were performed for two weeks. After these baseline assessments, participants were divided into two groups: one group performed combined training twice a week (G2x), and the other group three times a week (G3x). Both groups followed the same training program, which lasted 12 weeks, with the total exercise volume being higher in the group that trained three times per week due to the increased session frequency. All the assessments performed at baseline were repeated after 12 weeks.

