2.3. SUBJECTS

The participants in this study were individuals enrolled in the Cardiopulmonary Prevention and Rehabilitation Program (PROCOR) which is a community program for individuals with cardiometabolic risk factors offered by the Federal University of Santa Catarina (UFSC). This program provides specialized support for the safe practice of physical exercises and the promotion of cardiovascular health. Due to the structure of the program and the prior enrollment of participants, it was not possible to randomize the groups.

The inclusion criteria were being enrolled in the PROCOR program, having medical clearance to perform physical exercises, presenting one or more cardiometabolic risk factors, and having no physical limitations that could impair the execution of the proposed exercises.

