2.4. PROCEDURES

2.4.1. Training Protocol

The intervention was conducted with two groups following the same supervised combined training protocol, differing only in weekly frequency. The G2x group performed sessions on Tuesdays and Thursdays, while the G3x group participated in sessions on Tuesdays, Thursdays, and Fridays. The training program was carried out at the UFSC rehabilitation center and the strength training room, under the supervision of Physical Education professionals and students.

Initially, the participants underwent two weeks of familiarization aimed at introducing them to the Borg scale (6-20) and providing guidance on the correct execution of strength exercises. This process also sought to ensure proper adaptation to the protocol. The program was structured into three mesocycles, each lasting four weeks, with the goal of progressively increasing training intensity from one mesocycle to the next.

During strength training, participants performed four exercises: bench press, leg press, seated row, and hip abduction machine. Additionally, at the beginning of each mesocycle, load assessments were conducted, in which participants performed the first set at the lower limit of the repetition zone and in the second set, they were instructed to perform the maximum number of repetitions, both with the same load used during the previous mesocycle. As a safety precaution, the number of repetitions was limited to a maximum of 20. Based on the number of repetitions exceeding the lower repetition limit (RE), the load was adjusted to the mesocycle as follows⁽¹³⁾.

Upper limb exercises: Final weight (Kg) = weight used in the test (Kg) + RE/2

Lower limb exercises: Final weight (Kg) = weight used in the test (Kg) + RE

The aerobic training consisted of interval and pyramid workouts performed on treadmills. Intensity was prescribed using the Borg rating of perceived exertion scale (6-20), and higher intensities were achieved through variations in speed or incline. For those

training three times per week, two sessions were focused on speed variation, and one on incline variation. Participants trained twice per week, alternating between sessions of speed variation and incline variation.

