2.7. STATISTICAL ANALYSES

The data were analyzed using JASP (Version 0.19.3) [computer software]. The characterization variables had their normality and homogeneity tested using the Shapiro-Wilk and Levene tests, respectively. Variables classified as normal are presented as the mean and standard deviation. Categorical variables for characterizing the sample are presented as absolute frequency (sample n) and relative frequency (%). For comparing baseline characteristics between groups, the independent t -test was used for continuous

data and Fisher's exact test for categorical data. To compare adherence between groups, the Wilcoxon rank sum test was used, and data are presented as median and interquartile range (P25-P75).

For the comparison of the group (G2x and G3x) and time (pre-intervention and post-intervention), a 2-way analysis of covariance (ANCOVA) for repeated measures was performed, with the baseline values used as covariates. Outcomes were analyzed by intention to treat (ITT), which included all patients, once randomized, and missing data were imputed with simple imputation, replacing missing values with the last observed value. The significance adopted was 0.05.

REFERENCES

3. Penninx BWJH, Nicklas BJ, Newman AB, Harris TB, Goodpaster BH, Satterfield S, et al. Metabolic Syndrome and Physical Decline in Older Persons: Results from the Health, Aging and Body Composition Study. *J Gerontol A Biol Sci Med Sci*. 2009 Jan 1;64A(1):96–102.

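### Other physical activity is recorded at entry in a non-randomised comparison but left out of the outcome model, so an imbalance between G2x and G3x could bias the functional results in either direction.

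*Combined protocol and SAP*

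**What the plan says.** Section 2.1 describes an entry anamnesis that collected sociodemographic and health information "as well as to investigate their engagement in other physical activities". The document does not say how the answer is used afterwards.

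Section 2.3 states that randomisation was not possible because of the programme's structure and prior enrolment. Its inclusion criteria cover enrolment, medical clearance, risk factors and "having no physical limitations that could impair the execution of the proposed exercises". None concerns other exercise. The training protocol in 2.4.1 describes the groups as "differing only in weekly frequency" and says nothing about activity outside the programme.

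Section 2.7 compares the groups over time by repeated-measures ANCOVA "with the baseline values used as covariates". No other covariate is named. Baseline characteristics are compared between groups, but the variables are not listed.

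Section 2.1 also describes the two regimens "with the total exercise volume being higher in the group that trained three times per week", and gives the additional sessions as the reason.

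**The concern.** The planned difference is one session a week, Tuesday and Thursday against Tuesday, Thursday and Friday. The hypothesis in the Introduction is that three weekly sessions of "combined training would lead to better adaptations in cardiovascular risk factors and functional capacity than performing two weekly sessions". Regular exercise elsewhere could plausibly affect the same functional tests: sit-to-stand, arm curl, Timed Up and Go, sit-and-reach, 6-minute walk and 1000 m.

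Under randomisation, outside exercise would balance on average. Here it need not. If G2x participants are more active elsewhere, the benefit of a third session is understated. If G3x participants are, their outside exercise is credited to the programme. The outcome's baseline value is only a partial stand-in for outside activity, because it does not capture an effect on change during the 12 weeks.

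**Working it through.** The plan states no sample size, power, SD or outside-activity rate, so there is no figure of its own to reproduce. What follows is an illustration.

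**From the documents.** Two non-randomised groups; adjustment for the baseline outcome only; significance level 0.05 (taken as two-sided, since sidedness is not stated).

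**Assumed.** The third session has no true effect. Outside exercise is yes/no and worth 0.3 SD on the week-12 test. The baseline to week-12 correlation is 0.7. There are 30 or 60 participants per group. Outside exercisers make up 40% of one group and 10% of the other, or 80% and 20%. The 2.7 model is treated as an ANCOVA of the week-12 value on group and baseline.

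**Bias in the group difference**

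- Case A, outside exercise acts on week 12 and not on the baseline test: bias = 0.3 × (difference in proportions). This gives 0.3 × 0.30 = 0.09 SD and 0.3 × 0.60 = 0.18 SD.
- Case B, the same 0.3 SD is already in the baseline test: baseline adjustment removes the fraction 0.7, so bias = 0.3 × (difference in proportions) × (1 − 0.7). This gives 0.027 SD and 0.054 SD.

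**False-positive rate.** The standard error is approximately √(1 − 0.7²) × √(2/n) = 0.714 × √(2/n), which is 0.184 for n = 30 and 0.130 for n = 60. The rate is approximately Φ(b − 1.96) + Φ(−b − 1.96), with b = bias/SE. For case A, 80% v 20%, n = 30: b = 0.18/0.184 = 0.98, so the rate is about 16%. For case B, 80% v 20%, n = 60: b = 0.054/0.130 = 0.41, so the rate is about 7%. The table sets this approximation beside simulation (4,000 trials per setting; ranges show two separate runs).

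| Case | Imbalance | n per group | Bias (SD) | Approximation | Simulated |
|---|---|---|---|---|---|
| A | 40% v 10% | 30 | 0.09 | 7.8% | 8.4% |
| A | 40% v 10% | 60 | 0.09 | 10.6% | 9.4-9.9% |
| A | 80% v 20% | 30 | 0.18 | 16.4% | 14.3-15.5% |
| A | 80% v 20% | 60 | 0.18 | 28.2% | 25.9-26.8% |
| B | 40% v 10% | 30 | 0.027 | 5.3% | 5.0% |
| B | 40% v 10% | 60 | 0.027 | 5.5% | 5.5% |
| B | 80% v 20% | 30 | 0.054 | 6.0% | 5.2% |
| B | 80% v 20% | 60 | 0.054 | 7.0% | 6.5% |

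The approximation differs a little from simulation because it ignores the variance that outside exercise itself adds and the estimation of the residual variance.

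In case A, adding the outside-activity term brings the simulated rate back to about 5%. That assumes the entry answer is measured without error and describes activity throughout the 12 weeks. With equal proportions in both groups the bias formula gives zero in either case.

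**The case against.** The strongest reply is that the planned baseline covariate already does most of the work. Activity reported at entry is likely to be habitual. Habitual activity shows in the baseline test, which is case B: about 70% of the bias is removed and the error rate barely leaves 5%. This stands, and it limits the point. It does not dispose of it, because the documents do not show that outside activity is stable or that its effect is complete by entry.

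A second reply is that the trial is pragmatic and may leave usual activity free. This also stands as a matter of design. The question is the frequency of supervised combined training, and a G2x participant who also swims is still correctly analysed as receiving the twice-weekly programme. A reader might infer that such people are misclassified, so that the exposure itself is wrongly defined. The documents do not support that: outside activity is a confounder of a correctly defined comparison. Being pragmatic does not balance it, however, when allocation is not random.

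A reader might also infer that the contrast could be reversed. If an outside session counted the same as a programme session, the difference in total weekly sessions would be 1 + q3 − q2, where q2 and q3 are mean outside sessions in G2x and G3x. It turns negative only if q2 exceeds q3 by more than one session a week on average. The documents give neither mean, and they do not equate the two kinds of session.

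Third, an imbalance at entry is one instance of general confounding. That is true, but this confounder is one the plan already records.

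Finally, use of the variable cannot be ruled out altogether. Section 2.7 does not list the baseline characteristics it compares, and "All the assessments performed at baseline were repeated after 12 weeks" might be read to include the anamnesis, although it more naturally refers to the anthropometric, functional, hemodynamic and biochemical assessments. Neither reading puts an activity term in the outcome model. The public Appendix B shows no activity item, but its numbering passes from II to V and text may have been removed. The item's format is therefore unknown, and its absence there is not counted against the plan.

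**Conclusion.** The point holds as an unadjusted, recorded confounder in a non-randomised comparison. It can bias the functional results in either direction.

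The likely size runs from negligible to moderate. Bias is about 0.03-0.05 SD (error rate about 5-7%) if outside exercise is long-standing and already reflected in the baseline test. It is about 0.09-0.18 SD (about 8-26%) if outside exercise adds to change over the 12 weeks. Both ranges rest on the assumed imbalances, effect, correlation and group sizes; 80% v 20% is an extreme imbalance. The documents cannot say which case applies or whether any imbalance exists. The change is worth making because it is specific and nearly free, not because serious bias has been shown.

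**What to change.** - **Section 2.7, model.** Add other physical activity at entry, in the form the anamnesis recorded it, as a covariate beside the baseline outcome value in each functional outcome model.
- **Section 2.7, reporting.** Tabulate entry activity by group. If data collection is complete, both steps can still be done with the answers on file.
- **Week 12.** If the question is asked again, use that answer only descriptively or in a sensitivity analysis. Group may affect it, so it does not belong in the main model.
- **Wording.** State the conclusion as the effect of a third weekly PROCOR combined-training session. Read the volume statement in 2.1 as programme volume.

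The cost is SAP wording and about one degree of freedom per model (more if the item has several categories), with no extra participants or procedures. There are two limits. Self-reported activity is imprecise, so adjustment will be incomplete. An entry covariate also does not capture activity that starts or stops during follow-up.

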2.2. ETHICAL APPROVAL

The research was performed in accordance with the Declaration of Helsinki. This study was approved by the Ethics Committee for Research Involving Human Beings of the Federal University of Santa Catarina, Brazil (CAAE: 3.615.659), in accordance with Resolution 466/12 of the National Health Council on research involving human subjects.

2.3. SUBJECTS

The participants in this study were individuals enrolled in the Cardiopulmonary Prevention and Rehabilitation Program (PROCOR) which is a community program for individuals with cardiometabolic risk factors offered by the Federal University of Santa Catarina (UFSC). This program provides specialized support for the safe practice of physical exercises and the promotion of cardiovascular health. Due to the structure of the program and the prior enrollment of participants, it was not possible to randomize the groups.

The inclusion criteria were being enrolled in the PROCOR program, having medical clearance to perform physical exercises, presenting one or more cardiometabolic risk factors, and having no physical limitations that could impair the execution of the proposed exercises.

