2.5.4. Cardiorespiratory Fitness

Aerobic capacity was evaluated using two tests: the 6-minute walk test (6MWT), which participants completed one attempt, and the result was the total distance covered in that time⁽¹⁴⁾; and the 1000-meter test (1000m), that was developed due to the presence of a ceiling effect observed in the 6MWT in many participants in previous PROCOR training semesters, in which participants also made one attempt, and the score was the total time in seconds to complete the distance, allowing walking and/or running.

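### Earlier training in the same programme is neither restricted nor adjusted for in this non-randomised comparison, and it could move the G3x–G2x difference in either direction

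*Combined protocol and SAP*

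**What the plan says.** All participants come from PROCOR, a community programme of supervised exercise. Section 2.3 sets eligibility as follows: "The inclusion criteria were being enrolled in the PROCOR program, having medical clearance to perform physical exercises, presenting one or more cardiometabolic risk factors". The only further criterion concerns physical limitations. Nothing in the list refers to previous training in the programme, a break from training, or new versus returning status.

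The same section explains the allocation: "Due to the structure of the program and the prior enrollment of participants, it was not possible to randomize the groups".

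That the programme trained people before this study is clear from section 2.5.4. It introduces the 1000 m test because of a "ceiling effect observed in the 6MWT in many participants in previous PROCOR training semesters".

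Section 2.1 says that the anamnesis served, among other things, "to investigate their engagement in other physical activities". No later section gives that information a role. On follow-up it says: "All the assessments performed at baseline were repeated after 12 weeks". Section 2.4.1 adds a two-week familiarization with the exertion scale and exercise technique. Section 2.7 compares the groups with an ANCOVA whose only covariate is the outcome's baseline value.

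**The concern.** Someone who trained in PROCOR the semester before may enter with part of the training gain already made and with practice on the tests. A new entrant does not. The plan pools the two without counting them. Two separate consequences are possible.

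- **Effect modification.** If the benefit of a third weekly session differs between trained and untrained people, the pooled difference depends on the mix. This holds even when the mix is the same in both groups.
- **Confounding.** Groups were not randomised, so the returning share may differ between G2x and G3x. If returners gain less over 12 weeks, that imbalance alone produces a group difference.

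Baseline adjustment deals with the starting level. It does not deal with two people who have the same starting score but respond differently. At stake is the reading of the section 1 hypothesis that three sessions give better adaptations than two. Without the new/returning count, a reader cannot tell what population a null or positive result describes, or how much of it reflects the mix.

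**Working it through.** The documents give no sample size, effect size, SD, power or returning share, so there is no figure of the plan's to reproduce. Every input below is an assumption chosen to show the range.

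**1. Reference case.** Two-sided alpha 0.05 (the plan gives 0.05 without sidedness), 80% power, 1:1 allocation, difference 0.5 SD, normal approximation, no variance reduction from covariates:

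n per group = 2 × (1.960 + 0.8416)² / 0.5² = 2 × 7.849 / 0.25 = 62.8, so 63.

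**2. Same mix in both groups.** Let *f* be the returning share and *r* the fraction of the untrained G3x–G2x difference that returners keep. The pooled difference is multiplied by *m* = 1 − *f*(1 − *r*). Power with 63 per group is Φ(0.5*m*√(63/2) − 1.960) = Φ(2.806*m* − 1.960). The number needed for 80% power is 62.8/*m*².

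| *f* | *r* | *m* | Power with 63 per group | n per group for 80% |
|---|---|---|---|---|
| 0, or any | any, or 1 | 1.00 | 80% | 63 |
| 25% | 0.75 | 1 − 0.25 × 0.25 = 0.94 | 75% | 72 |
| 50% | 0.50 | 1 − 0.50 × 0.50 = 0.75 | 56% | 112 |
| 75% | 0.50 | 1 − 0.75 × 0.50 = 0.625 | 42% | 161 |

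The first row covers no returners (*f* = 0) or full response (*r* = 1). If frequency matters more in trained people, *r* exceeds 1, so *m* exceeds 1 and the pooled difference grows.

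**3. Different mix.** Let untrained gains be *g*₂ and *g*₃ (in SD), and let returners gain half as much. The observed difference in gain is *g*₃(1 − 0.5*f*₃) − *g*₂(1 − 0.5*f*₂).

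- No true difference, *g*₂ = *g*₃ = 0.5, returners 60% in G2x and 40% in G3x: 0.5 × 0.80 − 0.5 × 0.70 = +0.05 SD.
- The same gains with 75% and 25%: 0.5 × 0.875 − 0.5 × 0.625 = +0.125 SD. Reversing the shares gives −0.125 SD.
- *g*₂ = 0.5 and *g*₃ = 0.75, an untrained difference of 0.25 SD. Shares of 75% (G2x) and 25% (G3x) give 0.75 × 0.875 − 0.5 × 0.625 = 0.34 SD. The reverse gives 0.75 × 0.625 − 0.5 × 0.875 = 0.03 SD. With 50% in each group it is 0.75 × 0.75 − 0.5 × 0.75 = 0.19 SD.

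**4. What baseline adjustment removes.** Let returners start *d* SD higher, let *b* be the fitted slope of the 12-week value on baseline, and let Δ be the difference in returning share. The remaining bias has size Δ × [(gain gap) − (1 − *b*)*d*]. For the 75%/25% null case the gain gap is 0.5 − 0.25 = 0.25 SD and Δ = 0.50. With assumed *d* = 0.5 and *b* = 0.7, this is 0.50 × (0.25 − 0.3 × 0.5) = 0.05 SD, against 0.125 SD unadjusted. Adjustment helps here but does not remove the bias. If (1 − *b*)*d* exceeds the gain gap, the sign reverses.

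**The case against.** The strongest reply is that nothing shows this cohort had trained before. The prior enrolment in section 2.3 may mean only that people had signed up for a timetable slot, which fits its use there to explain why groups were not randomised. The ceiling sentence in section 2.5.4 concerns participants of earlier semesters, who may be other people, and the plan responded to that ceiling by adding the 1000 m test. Familiarization with the exertion scale and exercise technique suits newcomers at least as well as returners. This stands. A reader might infer that carry-over shrinks the adaptation under study, or that the trial really tests maintenance. The documents support neither.

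Second, smaller gains in both groups do not by themselves reduce the contrast. They do so only if frequency matters less in trained people, which the documents do not say. Returners might be the ones who need the extra session. The programme also raises intensity across mesocycles and resets loads individually, so a frequency effect near zero in returners would be an extreme assumption. This stands too.

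Third, the trial is pragmatic, and neither its objective nor its hypothesis is restricted to untrained people. A mixed population is a legitimate target, but the mix then has to be described.

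Fourth, the public version of Appendix B passes from part II to part V, so a training-history question may exist in parts III or IV, and asking about other activities does not prove that PROCOR history went unrecorded. Even so, section 2.7 gives such an item no role.

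Finally, stratum estimates for seven functional measures would mean 7 × 2 = 14 subgroup contrasts with no multiplicity plan. That is a good reason to keep them exploratory. It does not argue against one covariate.

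**Conclusion.** The point holds in conditional form. Established by the documents: recruitment from a programme with earlier training semesters, no randomisation, no eligibility limit on previous PROCOR training, and no adjustment beyond the outcome's baseline. Not established: that any participant was returning, how many were, how long since they last trained, or whether the groups differed in this.

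If returners were common, the 12-week gains and the pooled G3x–G2x difference may differ from those in untrained people. If their share was unequal, the comparison could be biased towards either group, and baseline adjustment cannot be relied on to remove that bias. On the assumed inputs, the first effect runs from no loss to a multiplier of 0.625 (80% down to 42% power), and the second reaches ±0.125 SD before baseline adjustment. These figures illustrate scale and do not estimate what happened in this trial. Limiting the conclusion on adaptations would be warranted only if returners prove common. The change is a cheap improvement to the analysis and does not mean that the comparison is invalid.

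**What to change.** 1. From PROCOR enrolment records (assumed to be available), classify each participant as new or returning before the outcome analysis. Define returning in advance, and record the number of earlier training semesters and the time since last training.
2. Report these by group alongside the other baseline characteristics.
3. In section 2.7, add new/returning status as a covariate, together with the baseline value, in the 12-week group comparison.
4. Give the group-by-status interaction, and the G3x–G2x estimate in new participants only, as sensitivity analyses labelled exploratory.
5. If returners are common, state that the pooled result applies to a mixed trained and untrained population. If nearly all were new, one sentence saying so settles the matter.

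Cost: one extra variable to extract, one model degree of freedom per outcome, and exploratory estimates that will be imprecise. No new recruitment or visits are needed.

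### The groups were not randomised, yet the SAP defines its ITT set by randomisation and adjusts only for baseline values, so the G3x–G2x comparison is open to uncontrolled confounding of unknown size and direction

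*Combined protocol and SAP*

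**What the plan says.** **Allocation.** Section 2.3 is explicit: "Due to the structure of the program and the prior enrollment of participants, it was not possible to randomize the groups". Section 2.1 gives the timing: "After these baseline assessments, participants were divided into two groups". Neither section says by what rule a participant entered one group or the other. Section 2.4.1 shows what separates the groups in practice: "The G2x group performed sessions on Tuesdays and Thursdays, while the G3x group participated in sessions on Tuesdays, Thursdays, and Fridays".

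**Analysis set.** Section 2.7 says: "Outcomes were analyzed by intention to treat (ITT), which included all patients, once randomized".

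**Model.** Section 2.7 specifies that "a 2-way analysis of covariance (ANCOVA) for repeated measures was performed, with the baseline values used as covariates". The abstract says the same. No other covariate, propensity method, matching or sensitivity analysis is named.

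**Baseline comparison.** Section 2.7 adds: "For comparing baseline characteristics between groups, the independent t -test was used for continuous" data, with Fisher's exact test for categorical data. It does not say what is done with the results.

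**The concern.** There are two faults, and they compound each other.

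First, the analysis set rests on an event that did not take place. As written, the population for every outcome is undefined, and the terms ITT and randomised suggest a protection against selection that this design does not have.

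Second, without randomisation, comparability of the groups has to come from the analysis. The plan provides only the baseline value. Participants in the two groups may differ in age, health, treatment or other exercise, and such factors can affect how much a person changes over 12 weeks. A significant G3x–G2x difference could then reflect who was in each group, and a null result could hide a real effect. The Introduction states a causal, directional hypothesis (three sessions better than two), and this one comparison has to carry it.

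**Working it through.** The plan gives no sample size, power, effect size, variance, allocation ratio or group data, so it has no figure to reproduce. The check is first textual, then illustrative.

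**Step 1: the analysis set.** Section 2.3 says nobody was randomised, and Section 2.7 includes patients once randomised. Taken literally, the set is empty. Several substitutes are possible: everyone enrolled in the programme, everyone assessed at baseline, everyone placed in a group, or everyone who began training. The plan does not choose among them. A baseline assessment is needed in any case, because missing values are replaced by the last observed value and the plan has only two assessments.

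**Step 2: what is collected and what is used.**

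| Factor | Where it appears | In the model? |
|---|---|---|
| Outcome's own baseline | Section 2.1 | Yes |
| Age (date of birth) | Appendix B | No |
| Sex | Implied by the sex-specific dumbbell, Section 2.5.1; no item in the form shown | No |
| Diagnoses | Appendix B | No |
| Medication | Appendix B | No |
| Other physical activity | Section 2.1; no item in the part of the form shown | No |
| Earlier programme participation | Earlier semesters mentioned in Section 2.5.4; no record shown | No |

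**Step 3: why baseline adjustment is not enough.** Let a factor U differ by d between groups. Suppose it shifts the baseline by 0.4 per unit, and the 12-week value by the same 0.4 plus a further 0.3 on change. All coefficients are assumed.

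- Within-group variance of the true level: 0.4² + 0.85² = 0.8825.
- Baseline variance, with error SD 0.4: 0.8825 + 0.16 = 1.0425.
- Covariance of baseline and follow-up: 0.8825 + 0.3 × 0.4 = 1.0025.
- Slope on baseline: 1.0025 / 1.0425 = 0.962.
- Bias after baseline adjustment: 0.7d − 0.962 × 0.4d ≈ 0.315d.

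For d = 0.3, 0.5 and 0.8 the bias is about 0.09, 0.16 and 0.25 outcome units. A simulation of follow-up-value ANCOVA (3,000 runs per cell, no true frequency effect) gave matching biases and these rejection rates at nominal 5%:

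| n per group (assumed) | d = 0.3 | d = 0.5 | d = 0.8 |
|---|---|---|---|
| 20 | 7.4% | 10.8% | 18.8% |
| 30 | 8.1% | 13.0% | 27.5% |
| 50 | 9.2% | 18.9% | 39.9% |

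Adding U to the model brought rejection back to 4.6%–5.5% and bias to about zero. That is the best case: one confounder, measured without error.

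**Step 4: generic sensitivity.** With residual bias b in residual SDs and SE = √(2/n), the two-sided rejection probability is Φ(b/SE − 1.96) + Φ(−b/SE − 1.96). For b = 0.2 and n = 30: SE = 0.258, b/SE = 0.775, and Φ(−1.185) + Φ(−2.735) = 0.118 + 0.003 = 12.1%.

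| n per group (assumed) | b = 0 | b = 0.1 | b = 0.2 | b = 0.3 | b = 0.5 |
|---|---|---|---|---|---|
| 20 | 5.0% | 6.2% | 9.7% | 15.8% | 35.3% |
| 30 | 5.0% | 6.7% | 12.1% | 21.3% | 49.1% |
| 50 | 5.0% | 7.9% | 17.0% | 32.3% | 70.5% |

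For a fixed bias, the error rate grows with sample size. The result also depends on the baseline–follow-up correlation r, since b is the bias divided by √(1 − r²). A bias of 0.125 outcome SD gives about 7% at n = 15, r = 0.5 (b = 0.144) and about 30% at n = 50, r = 0.9 (b = 0.287).

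**The case against.** The best defence is that the protocol is open about its design. Section 2.3 says plainly that the groups were not randomised, the abstract speaks only of dividing participants, and the false statement is a single phrase in Section 2.7. The plan also adjusts for baseline, which deals with much of any difference in starting level, and it tests other characteristics. This stands as far as it goes. But the phrase defines the population for every outcome, a non-significant baseline test does not show balance, and no test result changes the model. The words "with the baseline values used as covariates" could be read more widely than the outcome's own baseline, but no other variable is named.

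A reader might infer four stronger points, and the documents do not support them.

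- **That Sections 2.1 and 2.3 contradict each other on allocation.** Section 2.3 explains why randomisation was not possible; it does not say that prior enrolment decided the group. Dividing participants after baseline is compatible with that. The gap is an unstated rule.
- **That the comparison is confounded by who can attend three days.** This is an inference from prior enrolment and the added Friday session. Nothing says that participants chose their frequency, and no group data are given. Bias could favour either group.
- **That the sex-specific dumbbell itself biases the arm curl.** Each participant has the same load before and after, so the level difference is largely absorbed by the baseline. Sex may still modify response, which is reason enough to include it.
- **That the error rates above describe this trial.** Every input is assumed.

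Replacing baseline tests by standardised differences is a reporting preference and is not needed here.

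**Conclusion.** The concern holds in this form: a non-randomised comparison has an analysis set defined by randomisation and no confounder adjustment beyond baseline values. The wording conflict between Sections 2.3 and 2.7 is certain, and so is the absence of any other named covariate. It follows that the G3x–G2x comparison is open to uncontrolled confounding; that it is in fact biased, by how much and in which direction, cannot be determined from the documents. The illustrative error rates (about 6% to 70% for residual biases of 0.1 to 0.5 SD with 20 to 50 per group) show only that a modest leftover imbalance would matter. The point should be corrected before results are interpreted, because it affects every outcome and the remedy is cheap.

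**What to change.** 1. **Analysis set (Section 2.7).** Replace the randomisation-based definition with: *all participants allocated to G2x or G3x with a baseline assessment, analysed in the allocated group whatever their attendance*. State in Section 2.1 or 2.3 how and when allocation was made.
2. **Model (Section 2.7).** Add to each outcome model, whatever the baseline p-values, a short fixed list: age, sex, number of cardiometabolic conditions and other physical activity. For the blood pressure, lipid and glucose outcomes, add relevant medication. Add earlier programme participation only if it is on record. The document is written in the past tense and does not say whether outcomes have been examined; if they have, label the adjustment post hoc.
3. **Conclusions.** Word them as adjusted associations from a non-randomised comparison, and acknowledge that unmeasured factors such as motivation remain uncontrolled.

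**Cost.** This takes wording changes and one larger model per outcome, with no new visits. Most of the data are collected or known; the team should confirm that sex and other activity are recorded in usable form. With one term per factor, the list uses four degrees of freedom, or five with medication. At an assumed 30 per group in a follow-up-value ANCOVA, residual degrees of freedom would fall from 60 − 3 = 57 to 53 or 52. If the sample is much smaller, shorten the list, but fix it in advance. The causal claim becomes more modest.
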